**Print Principal Investigator Name: [name] MD MPH**

## **PRÉCIS**

### **Title: *Electronic-health Application To Measure Outcomes REmotely (EAT MORE) Clinical Trial***

#### **Study Objectives and Clinical Phase:**

This is a phase II feasibility, safety, tolerability and preliminary efficacy study of an e-Health application and in-person nutritional counseling to maintain or increase weight in patients with ALS and other neurodegenerative diseases.

#### **Objectives and Endpoints**

##### **Primary Objectives**

To study the feasibility, safety, tolerability and efficacy to maintain or increase body weight of an e-Health application and in-person nutritional counseling compared to standard of care and to each other.

##### **Secondary Objectives**

To measure the number of calories required to maintain or increase body weight in patients with neurodegenerative diseases.

**Tertiary Objectives:** To test the effects of an e-Health application compared to in-person nutritional counseling on survival, disease progression using the ALSFRS-R, UDysRS, or UHDRS, and on quality of life using the PROMIS SF v1.1 scale.

#### **Background and Rationale**

Progressive weight loss is a common symptom of ALS and other neurodegenerative diseases including Huntington's disease (HD) and Parkinson's disease (PD) and correlates with disease progression and time to death [1-3] [4, 5]. While nutritional interventions have been found to be effective in other chronic diseases including cystic fibrosis (reviewed in [6]) and COPD (reviewed in [7]), nutritional interventions have not been tested in a systematic way in neurodegenerative diseases.

Unintentional weight loss is common in ALS and is believed to be due to a combination of reduced caloric intake from dysphagia, anorexia, dependence on caregivers, and increased caloric needs due to increased energy expenditure [8, 9]. Kasarskis et al. first recommended increasing calorie intake in patients with ALS based on a retrospective review of ALS subjects close to the time of death, showing that these subjects consumed only 84% of the recommended daily allowance of calories [2, 10]. However the type of caloric intake and exact amount has not been adequately studied (reviewed in [11]). In our recently completed study, the Trial of High Fat/High Calorie Diet vs. Optimal Nutrition in ALS, funded by the Muscular Dystrophy Association[12], we found that participants randomized to excess calories and weight gain using a calorie-dense enteral formula had a reduced risk of dying during the study than patients randomized to calorie replacement. Given these promising results, we now wish to test whether an e-Health application designed specifically to promote hypernutrition will lead to weight gain, prevent weight loss and muscle loss, and improve survival and quality of life.

## **Study Design:**

This is a phase II feasibility, safety, tolerability and efficacy study of an e-Health application compared to in-person nutritional counseling and standard care. Approximately 150 ALS participants and approximately 75-150 PD and HD patients at MGH will be randomized 1:1:1 to one of three interventions: medical nutrition therapy using in-person counseling vs. the e-Health Application vs. standard care.

## **Interventions and Duration**

### **Administration of Intervention**

The goal of the two intervention arms (medical nutrition therapy using in-person counseling or using the e-Health Application) will be modest weight gain of 0.5-1 kg/month. Participants in the in-person nutritional counseling arm will receive an initial face-to-face nutrition counseling session according to a resource book outlining the general nutritional recommendations (see Appendix 1), as well as a personalized nutrition plan with daily caloric goals. They will then receive telephone monitoring of weight with additional telephone counseling as needed between return clinic visits. Home self-reported weights in both intervention arms will be verified at routine clinic visits. Patients in the in-person counseling arm will also receive in-person nutritional counseling at every clinic visit.

Participants in the e-Health arm will receive dietary guidance from the treating RD at the baseline visit including instruction in the completion of food records and weight monitoring using the e-Health App. They will be asked to enter their dietary intake and home weights every 2 weeks. The treating RD will also have access to the e-Health App data and will be able to modify the dietary recommendations of the application according to the recorded weights.

The standard care group will receive routine nutritional counseling by a treating physician or nurse about the importance of avoiding weight loss at regular clinic visits, as is the standard of care in our Neurology clinics.

A research coordinator will collect data on adverse events, disease progression, appetite and quality of life measures in all participants, including standard care participants at month 1 by telephone and at every clinic visit, approximately every 3 months. If participants are unable to make it to the clinic, the above measures will be collected by telephone interview. The total duration of the interventions will be 6 months.

## **Recruitment and Randomization**

Adult with ALS, PD or HD who come to the MGH Neurology clinics will be asked if they wish to participate in the study. Those who agree to participate will be randomized 1:1:1 to each of the three treatment arms using a computer generated randomization list generated by the MGH Biostatistics Center.

## **Statistical Methods**

Statistical analyses will be performed by the MGH Biostatistics Center. The primary and secondary efficacy outcomes of change in weight and caloric intake will be compared between the treatment groups using a shared-baseline linear mixed model for correlated, longitudinal assessments of weight with fixed effects of time and the treatment x time interaction and age, gender, and baseline dysphagia and their interactions with time included as covariates and random participant specific intercepts and slopes.

Safety data will be summarized by treatment group and reported to an independent Medical Monitor every 3 months during the study. Total numbers of adverse events will be compared between groups using negative binomial regression and the proportion of participants experiencing each type of event by Fisher's exact test.

In the tolerability analyses, a subject will be regarded as a treatment success if he/she complies with at least 80% of the nutritional counseling sessions, or enters at least 80% of the required electronic data.

Sample size calculation: Using the component estimates from weight data collected in the clinical trial of Ceftriaxone in ALS [13] the effective standard deviation for rate of change in weight assuming weight assessments every 2 weeks, an annual 23% mortality rate, and 20% loss to follow-up is 0.98 kg/month. Given a sample size of 150 ALS participants randomized 1:1:1 to the two interventions and standard care will provide at least 80% power to detect a true 0.75-kg/month difference between each intervention arm and the control arm over 24 wks at a two-tailed  $p < 0.027$  using Dunnett's method (testing superiority of each intervention over standard care). Based on a non-inferiority bound of 0.5 kg/month, the study will have at least 80% power to declare the e-Health intervention non-inferior to in-person consultation with an RD based on a one-tailed test at  $p < 0.05$  and assuming that the two interventions are in fact equivalent.

## LIST OF ABBREVIATIONS

AAN	American Academy of Neurology
AE	Adverse Event/Experience
ALS	Amyotrophic Lateral Sclerosis
ALSA	ALS Association
ALSFRS-R	Amyotrophic Lateral Sclerosis Functional Rating Scores – revised
BMI	Body Mass Index
CNAQ	Council on Nutrition Appetite Questionnaire
CRF	Case report form
CFR	Code of Federal Regulations
CNS	Central nervous system
CRC	Clinical Research Center
DM	Data Management
eCRF	Electronic Case Report Form
EDC	Electronic data capture
FDA	Food and Drug Administration
GCP	Good Clinical Practice
HD	Huntington’s Disease
ICH	International Conference on Harmonisation of Technical Requirements for Registration of Pharmaceuticals for Human Use
IRB	Institutional Review Board
MDA	Muscular Dystrophy Association
MedDRA	Medical Dictionary for Regulatory Activities
MGH	Massachusetts General Hospital
MGH-SST	MGH Swallow Screening Tool
MM	Medical Monitor
MND	Motor neuron disease
MRC	Medical Research Council
NCRI	Neurology Clinical Research Institute
NIH	National Institutes of Health
NINDS	National Institute of Neurological Disorders and Stroke
NP	Nurse Practitioner
ODBC	Open Database Connectivity
OHRP	Office for Human Research Protections
PAV	Permanent assisted ventilation
PD	Parkinson’s Disease
PDF	Portable Document Format
PI	Principal Investigator
PROMIS SF v1.1	Patient Reported Outcome Measurement Information System Short Form
RD	Registered Dietitian
SAE	Serious adverse event
SDF	Source Document Form
SLP	Speech Language Pathologist
UDysRS	Unified Dyskinesia Rating Scale
UHDRS	Unified Huntington’s Disease Rating Scale
VC	Vital capacity
WHO	World Health Organization

**Table 1. Schedule of Activities**

Schedule of Activities	Screening/ Baseline	2 week Automatic Alerts	Telephone Visits (every 2-4 weeks)	In-Person Visits (3 and 6 months +/- 1 month)
All Participant Groups including Standard Care				
Written Informed Consent	X			
Abbreviated History/Weight history	X			
MGH Swallow Screening Tool	X			X
Inclusion/Exclusion review	X			
Adverse Events			X 	X*
Vital Signs including Height, Weight	X			X
Clinical Laboratory Assessments	X 			X 
Disease-specific rating scales (ALSFRS-R, UDysRS, UHDRS)	X*			X*
PROMIS SF v1.1	X*			X*
CNAQ	X*			X*
Dietary Intake using 24 hour recall	X			
Dietary Intake using 4 day food records	X			X
DXA Scan (optional)	X			X (month 6 only)
In-Person Nutritional Counseling				
Nutritional Counseling per Protocol	X		X	X*
Dietary Intake using 4 day food records			X (by fax)	
Weight	X		X†	X
e-Health Application Arm				
4 days of Dietary Intake using the e-Health App	X	X		
Weight (2 days)	X	X†		X

 Adverse events and changes in concomitant medications will be obtained by the research coordinator telephone interview in all participants 1 month after the start of the study, including the Standard Care arm. Adverse events will also be captured at every telephone contact by the Registered Dietitian in the In-Person Nutritional Counseling arm.

 Screening labs to include basic chemistry, liver function tests, lipid panel, thyroid stimulating hormone (TSH), uric acid, albumin, and exploratory labs including leptin, PYY and ghrelin.

 Routine Safety labs to include basic chemistry, liver function tests, lipid panel, albumin and hemoglobin A1c. Six month labs will also include exploratory labs (leptin, PYY and ghrelin).

 Labs drawn within 4 weeks of visit for clinical or research purposes may be used for the study

\* May be administered or obtained by telephone within 1 week of the scheduled in-person visit if participants are unable to come to the clinic or too fatigued to complete during their clinic visit. If participants are unable to come to clinic, a self-reported home weight will be obtained and marked as self-reported.

† Participants will weigh themselves at home following specific instructions.

Abbreviations: ALSFRS-R= Amyotrophic Lateral Sclerosis Functional Rating Scale-Revised; UDysRS= Unified Dyskinesia Rating Scale; UHDRS= Unified Huntington's Disease Rating Scale; PROMIS SF v1.1= Patient Reported Outcome Measurement Information System Short Form; CNAQ= Council on Nutrition Appetite Questionnaire;

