### ***5.3 Monitoring of Weight***

Weight will be assessed at every clinic visit in all three groups. Participants in both intervention arms will be asked to weigh themselves at home or in a clinic or allied health professional office every 2-4 weeks and either enter their weights into the e-Health app or in to their Self-Weighing Log. Participants in the in-person arm will be instructed to report significant weight changes by phone to their clinic RD. The clinic RD may modify the dietary recommendations at any time based on observed weight loss, adverse events, or at their discretion. Persistent weight loss despite >90% dietary compliance will prompt an increase in target calories by 235 Kcal/day, or more if the weight loss is more than 0.5 kg/week. Changes in the dietary recommendations will be recorded in the EDC.

Any weight loss >1.5 kg during the study will prompt an increase in the frequency of telephone contact and an appropriate increase in the recommended caloric goals. In addition, any report of weight loss will prompt the treating dietitian to explore (by telephone) whether this is due to unwillingness to continue participation in the trial, inability to comply with the prescribed diet (due to weakness, dysphagia, or dependence on caregivers), or inadequate caloric recommendations. Reported dysphagia (using the swallow screening questionnaire, Appendix 9) will prompt the treating RD to refer the patient for an early in-person evaluation by their medical providers. Participants who lose more than 3 kg despite non-invasive attempts to maintain body weight will be referred to a Speech Language Pathologist for evaluation of dysphagia and possible consideration of a feeding tube.

All participants who require a feeding tube during the study will be prescribed enteral nutrition based upon results of the High Fat/High Calorie diet study. Jevity 1.5 will be prescribed at 1.5 times their calculated TDEE using the HB equation, adjusted for a self-reported activity factor [39]. Given the safety and tolerability results of this study, we do not feel that it is ethical to use a control or eucaloric diet in the standard care arm.

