#### **6.1.2 Telephone Visits (Every 2-4 weeks)**

The Research Coordinator on the study will contact all participants by telephone at month 1 in all arms to determine if there have been any adverse events. The Coordinator will also contact participants by telephone who are unable to return to the clinic for their routine clinic visits, in order to perform disease-related outcome measures and the quality of life questionnaire.

After the initial screening/baseline visit, the treating Registered Dietitian will monitor dietary intake and weight in the in-person arms every 2-4 weeks as necessary based upon observed weight changes. They will monitor dietary compliance by having participants complete paper food records and faxing them along with the Self-Weighing Log for review. They will then contact participants by telephone to query any weight loss or emergence of adverse events. If the treating RD identifies weight loss despite >90% compliance with dietary recommendations, they will adjust their dietary recommendations to meet the target weight from Table 2. They will then contact the study participant at least once every 2 weeks until the participant's weight has stabilized or increased. The frequency and duration of counseling sessions will be documented in the EDC.

The RD in the e-Health Application arm will contact participants who report weight loss through the App directly, through email, or by telephone if necessary. The RD will assess whether the weight loss is due to an inability to comply with the prescribed diet (due to weakness, dysphagia, or dependence on caregivers), versus inadequate caloric recommendations. Symptoms of dysphagia using the self-reported swallow screening questionnaire will prompt the treating RD to refer the patient to SLP for an early in-person evaluation.

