### **9.1 *Safety and Tolerability***

All randomized subjects will be considered evaluable for tolerability and safety. Subjects lost to follow-up will be considered treatment failures at the time they drop out of the study. The data will be reviewed by the independent Medical Monitor, using the considerations here as guidelines. Their recommendation would then be reviewed by the Principal Investigator.

Safety data will be summarized by disease group and treatment group and reported to the independent Medical Monitor every 3 months during the study. Total numbers of adverse events will be compared within each disease group and among treatment groups using negative binomial regression and the proportion of participants experiencing each type of event by Fisher's exact test. Every 3 months the Medical Monitor will review cumulative study reports to determine if there has been an excess rate of serious adverse events in any of the arms. At two interim analyses, mortality rates will be compared, and one or both intervention arms may be terminated for one or more disease groups according to pre-determined stopping rules described below.

In the tolerability analyses, a subject will be regarded as a treatment success if he/she complies with at least 80% of the nutritional counseling sessions, or enters at least 80% of the required electronic data.

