## **10.5 Adverse Experiences Monitoring and Reporting**

An adverse event (AE) is any unfavorable and unintended sign (including a clinically significant abnormal laboratory finding, for example), symptom, or disease temporally associated with a study, use of a drug product or device whether or not considered related to the drug product or device.

The adverse event (AE) definitions and reporting procedures provided in this protocol comply with all applicable U.S. FDA and ICH guidelines and regulations. The Principal Investigator will carefully monitor each subject throughout the study for possible adverse events. All AEs will be documented on eCRFs designed specifically for this purpose. It is also important to report all AEs, especially those that result in permanent discontinuation of the investigational drug being studied, whether serious or non-serious.

Subjects will be monitored for adverse events from the time they sign consent until completion of their participation in the study. For the purposes of this study, symptoms of progression/worsening of ALS, PD and HD including ‘normal’ progression, will not be recorded as adverse events. Relationship of adverse experiences to the experimental intervention will be assessed at each in-person and telephone study visit by recording all voluntary complaints of subjects and by assessment of the medical. Attention will be directed to clinical adverse experiences associated with the prior hypercaloric dietary intervention, as well as any evidence of unexpected worsening of the underlying disease. Laboratory surveillance tests will be obtained as outlined above.

A serious adverse event is defined as an adverse event that meets any of the following criteria:

- Results in death
- Is life threatening: that is, poses an immediate risk of death as the event occurred. This serious criterion applies if the study subject, in the view of the Site Investigator, is at substantial risk of dying from the AE as it occurs. It does not apply if an AE hypothetically might have caused death if it were more severe.
- Requires inpatient hospitalization or prolongation of existing hospitalization. Hospitalization for an elective procedure (including planned tracheostomy) or a routinely scheduled treatment is not an SAE by this criterion because a “procedure” or a “treatment” is not an untoward medical occurrence.

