### **10.5.1 Evaluating and Recording of Adverse Events**

At each visit all adverse events that are observed, elicited by the Principal Investigator, or reported by the subject will be recorded in the appropriate section of the Adverse Event log, entered into the EDC and evaluated by the Principal Investigator.

Adverse events will be categorized according to the MedDRA coding system. This is a descriptive terminology, organized by body system and including specific criteria for grading severity of Adverse Events. This system will allow study coordinators to quickly search for the most relevant term for each event and will give specific criteria governing the reporting of severity for each term. With this system, the event will be coded at the site and subsequently checked by the Data Manager.

Minimum information required for each AE includes type of event, duration (start and end dates), severity, seriousness, causality to study intervention, action taken, and outcome.

---

The relationship of the AE to the study intervention should be specified by the Site Investigator, using the following definitions:

1. Not Related: Concomitant illness, accident or event with no reasonable association with treatment.
2. Unlikely: The reaction has little or no temporal sequence from administration of the study intervention, and/or a more likely alternative etiology exists.
3. Possibly Related: The reaction follows a reasonably temporal sequence from administration of the intervention and follows a known response pattern to the suspected intervention; the reaction could have been produced by the study

intervention or could have been produced by the volunteer's clinical state or by other modes of therapy administered to the volunteer.

4. **Probably Related:** The reaction follows a reasonable temporal sequence from administration of study intervention; is confirmed by discontinuation of the study intervention or by rechallenge; and cannot be reasonably explained by the known characteristics of the volunteer's clinical state.
5. **Definitely Related:** The reaction follows a reasonable temporal sequence from administration of study medication; that follows a known or expected response pattern to the study medication; and that is confirmed by improvement on stopping or reducing the dosage of the study medication, and reappearance of the reaction on repeated exposure.

---

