- 3) Quality of life as measured using the PROMIS SF v1.1 will be compared between the treatment groups using a shared-baseline linear mixed model for correlated, longitudinal assessments of PROMIS with fixed effects of time and the treatment x time interaction and age, gender, duration of disease and their interactions with time included as covariates and random participant specific intercepts and slopes.

Safety data will be summarized by treatment group. Total numbers of adverse events, categorized by organ system, will be compared between groups using negative binomial regression and the proportion of participants experiencing each type of event by Fisher's exact test.

Tolerability will be measured in two ways:

- 1) The amount of engagement that participants exhibited as measured by the number of interactions they had with a dietitian and the number of times that they interacted with the app,
- 2) The length of trial involvement as measured by the time to the last interaction with a dietitian (in-person or by App). Many participants were lost to follow-up (need to make sure documented). Participants who came to clinic visits only (seeing RD) but

did not engage otherwise, their last date of engagement is recorded in the Final Disposition form under "loss to follow-up"

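### Only the in-person arm is asked about adverse events at dietitian calls, and the planned between-arm comparisons make no allowance for it

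*Protocol*

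**What the plan says.** **Contacts common to all arms.** The coordinator asks about adverse events by telephone at month 1, at the month 3 and 6 clinic visits, and by telephone one month after the final visit (Protocol Table 1, Sections 6.1.2, 6.1.5 and 6.2.1.1).

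**Additional contacts, in-person arm.** Footnote 1 to Table 1 states: "Adverse events will also be captured at every telephone contact by the Registered Dietitian in the In-Person Nutritional Counseling arm". Section 6.1.2 makes this an active question. Dietitians review food records and weights every 2 to 4 weeks as needed, and: "They will then contact participants by telephone to query any weight loss or emergence of adverse events". Calls rise in number when weight falls; Section 5.3 says: "Any weight loss >1.5 kg during the study will prompt an increase in the frequency of telephone contact".

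**Other arms.** In e-Health, dietitian contact follows reported weight loss (Section 6.1.2) or a change of more than 2 pounds (Section 6.2.1.2), and no question about adverse events is specified. Standard care is counseled by a physician or nurse at clinic visits (Section 5.1.3).

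**Recording.** Under Section 10.5, the relationship of adverse experiences to the intervention is "assessed at each in-person and telephone study visit by recording all voluntary complaints of subjects". Under Section 10.5.1, events observed, elicited or reported at each visit "will be recorded in the appropriate section of the Adverse Event log, entered into the EDC and evaluated by the Principal Investigator".

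**Analysis.** Protocol Section 9.1: "Total numbers of adverse events will be compared within each disease group and among treatment groups using negative binomial regression". SAP: "Total numbers of adverse events, categorized by organ system, will be compared between groups using negative binomial regression". Both add Fisher's exact test on the proportion with each type of event. Neither names a reporting source, restricts to common contacts, or plans a sensitivity analysis for unequal querying.

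**The concern.** A mild event that starts and resolves between two coordinator contacts reaches the log only if the participant remembers it at the next contact. In standard care that can be about three months later, whereas an in-person participant will often have been asked within 2 to 4 weeks. With equal true rates, the in-person arm would then show more recorded events, and the planned tests cannot separate that from a real difference.

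Safety is one of the primary aims, with the interventions compared both to standard care and to each other (Section 1.1). The negative binomial and Fisher comparisons are the only between-arm adverse-event tests in the SAP. The trial is open label (Section 4.4.2), so blinding does not even out reporting. Because calls increase after weight loss, the extra capture is also linked to the primary efficacy outcome.

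**Working it through.** The documents give no figure for completeness of adverse-event capture, so there is nothing to reproduce. The check has a part that rests on the documents (steps 1 and 2) and an illustrative part (steps 3 to 5).

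**1. Scheduled occasions on which events are asked about.** Standard care and e-Health: 4. In-person: 4 coordinator contacts plus dietitian calls over about 26 weeks.
- Calls every 4 weeks: 26/4 = 6.5, so 6 calls; 4 + 6 = 10.
- Calls every 2 weeks: 26/2 = 13 calls; 4 + 13 = 17.

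Some calls may fall close to coordinator contacts, and not all need be made.

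**2. Route to the analysis.** All reports go to one log and the EDC (Section 10.5.1), and the tests use totals and event types (Section 9.1, SAP). No step removes the extra reports.

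**3. Illustrative recorded ratio with equal true rates.** Inputs from the documents: contact timing (coordinator at 4.3, 13.0, 26.1 and 30.4 weeks; calls every 2 or 4 weeks to month 6). Assumed: onset uniform over 30.4 weeks, exponential event duration, calls made 100% or 50% of the time at random, and full follow-up. An event still present at the next contact is recorded; otherwise

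P(recorded) = 0.5^(weeks from resolution to next contact / recall half-life).

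The table gives in-person / standard-care ratios from 400,000 simulated events per scenario.

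| Mean duration | Half-life | All calls, 2-weekly | All calls, 4-weekly | Half of 2-weekly | Half of 4-weekly |
|---|---|---|---|---|---|
| 4 wk | 4 wk | 1.30 | 1.25 | 1.22 | 1.15 |
| 4 wk | 8 wk | 1.17 | 1.14 | 1.13 | 1.09 |
| 4 wk | 13 wk | 1.11 | 1.09 | 1.08 | 1.06 |
| 4 wk | 26 wk | 1.05 | 1.05 | 1.04 | 1.03 |
| 8 wk | 4 wk | 1.18 | 1.15 | 1.13 | 1.09 |
| 8 wk | 26 wk | 1.04 | 1.03 | 1.03 | 1.02 |
| none (does not persist) | 4 wk | 1.61 | 1.44 | 1.39 | 1.24 |
| none (does not persist) | 26 wk | 1.09 | 1.07 | 1.07 | 1.04 |
| any | complete recall | 1.00 | 1.00 | 1.00 | 1.00 |

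In the 1.30 cell, about 97% of events are recorded in the in-person arm and about 75% in standard care (0.970/0.746 = 1.30). A repeat run agreed with the table to within 0.01.

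**4. Effect on the tests.** 150/3 = 50 ALS participants per arm. The documents set no significance level for adverse events; two-sided 5% is assumed, with mean m = 2 to 8 events per participant and dispersion k = 0.5 to 1.0. For the negative binomial Wald test at recorded ratio R,

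SE = √[(1/m + 1/(mR) + 2k)/50], z = ln R / SE, rejection rate = P(Z > 1.96 − z) + P(Z < −1.96 − z).

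- R = 1.30, m = 2, k = 1: SE = √[(0.500 + 0.385 + 2)/50] = 0.240; z = 0.262/0.240 = 1.09; rejection about 19%.
- R = 1.30, m = 8, k = 0.5: SE = √[(0.125 + 0.096 + 1)/50] = 0.156; z = 0.262/0.156 = 1.68; rejection about 39%.

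| Recorded ratio | Negative binomial | Fisher, single event type |
|---|---|---|
| 1.00 | 5% | 3–4% |
| 1.10 | 7–9% | not calculated |
| 1.20 | 12–21% | 4–7% |
| 1.30 | 19–39% | 6–13% |

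The Fisher column assumes 0.3 to 1.0 events of a type per participant and dispersion 0 to 1.0. Fitting 1,500 negative binomial models per cell gave similar rates: 5–6%, 8–10%, 13–23% and 21–40%.

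**5. Common contacts only.** If only events reported at the four coordinator contacts are counted, the expected ratio in this kind of model is 1.00, provided the dietitian calls do not improve later recall.

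**The case against.** **The main safety outcomes are little affected.** Section 6.2.1.1 defines safety by hospitalizations, deaths, other serious events and discontinuations due to adverse events. The Medical Monitor looks for excess serious events (Section 9.1), and the only formal stopping rule concerns mortality (Section 9.5). No significance level or decision rule is attached to non-serious counts. This stands and limits the severity. A reader might infer that the stopping rule or the trial's safety conclusions as a whole are undermined; the documents do not support that.

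**More complete capture is not false capture.** A reader might infer that the in-person arm records spurious events. Nothing in the documents points to that, and in the model its capture never exceeds 100%. The shortfall lies in the other arms.

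**Other arms have contacts too.** The Section 5.3 rules on weight loss are not confined to the in-person arm, e-Health weight changes alert the dietitian (Section 6.2.1.2), and Section 10.5 provides for recording voluntary complaints at study visits. Section 6.1.1 tells participants, without naming an arm, to contact the site after losing 3 or more pounds, although Sections 5.3 and 6.2.1.2 describe home weighing and the log more narrowly. These contacts may narrow the gap, especially for e-Health. They are triggered, carry no specified question about events, and so do not equalise capture.

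**The size is assumed.** True. Recall, duration, event rate and dispersion are not in the documents, and the model ignores both the link between calls and weight loss and loss to follow-up. The SAP notes: "Many participants were lost to follow-up (need to make sure documented". Unequal loss could shrink, enlarge or reverse the ratio.

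**Conclusion.** The concern holds for non-serious adverse events. Only the in-person arm has a scheduled active query beyond the common coordinator contacts, and the planned comparisons ignore it. Unless recall is complete, events are captured less fully in standard care, and probably in e-Health, so with equal true rates and similar follow-up the in-person arm would appear to have more events. The contrast with standard care is the clearest.

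The direction follows from the documents; the size is unknown. With a mean duration of 4 weeks and recall half-lives of 4 to 26 weeks, the recorded ratio is 1.05–1.30 if all calls are made and 1.03–1.22 if half are. It nears 1.6 only if events do not persist, the half-life is 4 weeks and every 2-weekly call is made. A reader might take that extreme as the likely distortion; the documents hold no data on recall, event duration or calls made that would support it. Single event types tested by Fisher's exact test are less affected than totals. Severity is minor to moderate, and the remedy is cheap.

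**What to change.** **If the AE form lets events be attributed to a contact, or collection is still open:** state in the SAP that the negative binomial and Fisher comparisons use all events reported at the common coordinator contacts, asked identically in every arm and counted whether or not a dietitian logged them first. List events known only from dietitian contacts, in either intervention arm, separately. The minimum fields in Section 10.5.1 do not include the reporting contact, so the form must be checked.

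**If attribution is not possible:** base between-arm safety inference on deaths, hospitalizations and other serious events. State that non-serious contrasts involving the in-person arm are descriptive because of unequal querying. Report e-Health versus standard care with the caveat that triggered dietitian contacts may add e-Health events.

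**Two things to avoid:**
- Discontinuation due to adverse events should not carry inference against standard care. That arm has no comparable study intervention to discontinue (Section 5.1.3), and reasons are documented partly by the dietitian (Section 6.1.4).
- The number of dietitian contacts should not be used as a covariate. It arises after randomization and rises with weight loss (Sections 5.3 and 6.1.2).

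**Cost:** one SAP paragraph and no new data. If collection is open, add a common coordinator script and one contact field on the AE form. The SAP describes loss to follow-up in the past tense, so collection was probably well advanced or complete. The price is fewer in-person events in the test, or no formal test for those contrasts. Some bias may remain if dietitian calls improve later recall.
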